6.1. Preoperative and Intraoperative Period

Parents and patients will be asked to complete a questionnaire prior to the child's surgery. This will take approximately 5 minutes. Participants can choose to complete the survey and not participate in the randomized part of the study. The questionnaire is to determine if factors such as anxiety and social economic attributes interact with each other prior to surgery. If only participating in the questionnaire information regarding demographic data, pain scores and pain treatment will be collected from the patients' medical record.

Patients will receive standard physiologic monitoring for anesthesia and postoperative care. Using a modified Dixon up and down dose finding method, subjects in the first cohort are randomized 1:2 to receive either control (standard intraop opioid) or methadone HCl (0.4 mg/kg ideal body weight, IBW). In the second cohort, subjects are randomized 1:2 to receive either control (standard intraop opioid) or methadone HCl (0.3 mg/kg ideal body weight, IBW).

Anesthesia and surgical care will not be altered for the purposes of this investigation, except that subjects in groups I and II, will receive methadone as their intraoperative opioid, rather than leaving the choice of intraoperative opioid to the anesthesiologist (patients typically may get methadone or any other opioid). The control group patients will receive intraoperative analgesia with opioids other than methadone left at the discretion of their anesthesiologist. Additional

randomized cohorts may be included to study IV methadone HCl doses within the range of 0.3 – 0.5mg/kg IBW, based on interim study findings and analysis.

6.2. *Administration of Study Medication.*

Methadone is administered as an IV bolus after induction of anesthesia and after an arterial line is placed. Methadone hydrochloride is available commercially as a solution for injection of 10 mg/ml. Based on our experience, we believe that additional postoperative opioids will still be needed, but that increasing methadone doses will result in lessened postoperative opioid use.

6.3. *Assessments.*

6.3.1. Pain Assessment – Acute postoperative pain will be managed by St. Louis Children's Hospital pain services. Assessments are made in the postoperative period by a trained member of the research team blinded to intraoperative use of methadone. These will be conducted on each post-operative day until discharge or post op day 6, whichever comes first. Pain intensity is assessed using the Wong-Baker FACES scale employed by the inpatient nursing staff and previously validated (9). Pain relief is also assessed using a Colored-Visual Analog Scale. Other questions regarding pain relief and comfort may be given using a tablet. Sedation is assessed using a five-point scale (patient fully alert – not arousable). Itching and nausea are assessed using a five-point verbal scale (none, mild, moderate, severe or excruciating).

6.3.2. Pharmacokinetics – Pharmacokinetics studies will be performed for all patients in methadone treatment groups. Blood samples (approx 3 ml each) will be obtained before methadone and at approx 0.08, 0.5, 1, 1.5, 2, 3, 4, 6, 8, 10, 12, 24, 48, 72, and 96 hr after IV methadone administration. Blood samples will be drawn from the arterial line for the first 24 hours and then from the venous lines or collected with routine labs. Total amount of blood drawn will be approx. 48 mls for pharmacokinetic testing for up to four days. Blood will only be collected while the patient is hospitalized; if the patient is discharged from the hospital no further collections will be made.

6.3.3. CYP Genotyping – For all patients, 5 ml of blood will be drawn for CYP2B6 genotyping. Genotyping will be performed at the WUSTL Genome Technology Access Center (GTAC).

6.3.4. Urine samples- For all patients, 24 hour- urine collections will be conducted for up to 96 hours after surgery.

6.4. *Postoperative Period*

Patients receive standard of care analgesia using patient control analgesia method, primarily with hydromorphone or morphine as determined by the treating physician. Postoperative

care is not altered for purposes of this study.

7. Data Collection and Monitoring.

- 7.1. *Assessment of Pain Intensity and Pain Relief*- Each pediatric patient enrolled in the study, regardless of type of opioid received, will have pain intensity assessed each post operative hospital day (HD) for up to six days or until discharge, whichever comes first. The Wong-Baker FACES scale and Verbal analogue scale, available as laminated cards, are currently used by the nursing staff to assess pain on the inpatient units. Pain will also be assessed by patients using a colored-visual analogue scale. The study personnel performing the assessment will have a set script to read when administering the scale.
- 7.2. *Opioid Consumption*. The inpatient medical record will be used to calculate the amount of morphine or morphine equivalents administered for each 24-hour period that subjects are receiving opioid analgesics. Oral opioid administration will be totaled through discharge for each 24-hour period as well.
- 7.3. *Other Required Studies*. Required baseline measurements that will be obtained from the EMR are vital signs, weight, height, and peripheral oxygen saturation by pulse oximetry and are all collected as standard of care.
- 7.4. *Drug and metabolite concentrations and drug effects*. Plasma concentrations of methadone and the mono N-demethylated metabolite EDDP will be determined by HPLC-mass spectrometry.
- 7.5. *Sources of Research Material*. Background information including demographic data, outpatient medications used, and chronic medical conditions will be obtained from the medical record at the time of enrollment

8. Data and Safety Monitoring Plan.

In general, the PI has developed a specific set of Standard Operating Procedures (SOPs) for clinical research. All individuals working under the PI are required to read and be totally familiar with and compliant with the SOPs. The PI's SOPs are in part developed from and are compliant with the Institutional guidelines, including those for a) Interactions with the Washington University Human Subjects Review Committee, b) Informed Consent Development and Implementation, c) Subject Recruitment and Screening, d) Subject Management While on Study, e) Adverse Event Reporting.

- 8.1. The specific monitoring plan for this investigation is commensurate with the risks and the size and complexity of the investigations planned. The potential risks are attributable to the use of methadone. Based on these considerations the monitoring plan involves engaging one colleague (a pediatric anesthesiologist, pediatrician or clinical pharmacologist knowledgeable in the pharmacology of opioids) not involved in the study to serve in a monitoring capacity. Based on

the small size and relatively low risks nature of the protocol, only a third person (the colleague), rather than a full DSMB, is utilized. This individual will review the annual summary of adverse events. In addition, they will review all reports of a Serious Adverse Event, or an Unexpected Adverse Event.

- 8.2. The specific plan for submitting Adverse Event Reports to the IRB is detailed in the PI's SOP for Adverse Event Reporting.
- 8.3. *Off-Study Criteria:* Participation will be terminated if requested by the patient or patient's guardian().
- 8.4. *Stopping Rules:* The study will be temporarily suspended, pending a detailed review, if there is a Serious Adverse Event resulting from methadone.

9. Statistical Methods

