Methadone in Pediatric Anesthesia II

PI: [name] MD, MBA
Associate Professor,
Director of Quality Improvement,
Department of Anesthesiology, BO 8054
[contact]
[contact]

Co-PI: [name] PhD
Russell D. and Mary B. Shelden Professor of Anesthesiology
Director, Division of Clinical and Translational Research
Department of Anesthesiology, Box 8054
T [contact]
F [contact]
[contact]

Co-Investigators: [name] MD
Associate Professor of Anesthesiology
Box 8054,
[contact]

Original: 02/02/2013
Amendment 1: 12/5/13
Amendment 2: 4/16/14
Amendment 3: 09/10/2014

Amendment 1, 12/5/2013: Administration of PROMIS questionnaire to be administered by the research team to the patient on a tablet device.

Rationale: To help determine patient's preoperative expectations and functional status as impacted by their medical condition requiring this surgical procedure.

CONFIDENTIAL

Amendment 2, 4/16/2014: Administration of a questionnaire to the participant's parent or legal guardian

Rationale: To help determine from the primary caregiver the influence of the environment, social and psychological, on post-operative pain.

CONFIDENTIAL

Amendment 3, 09/10/2014: Change in dosage range for intraoperative administration of methadone from 0.4-0.5mg/kg Ideal Body Weight to 0.3 – 0.5mg/kg Ideal Body Weight (IBW)

Rationale: Postoperative management of pain for the pediatric spinal surgery population has changed over the course of time since the completion of our last research project (HRPO# 201107357). The previous study had demonstrated that 0.3mg/kg methadone was not effective in reducing postoperative opioid consumption. Currently, patients are prescribed additional drugs such as gabapentin and methocarbamol, with potential for interaction with all opioids. Based on our observations with this current protocol to date, we anticipate that escalation of methadone dosages beyond 0.4mg/kg (ideal body weight) may not be required. We feel that routine postoperative use of gabapentin and methocarbamol require re-evaluation of intraoperative methadone dosing at 0.3mg/kg (IBW) for this population under current standard of care pain management.

CONFIDENTIAL

Abstract

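### Inpatient non-opioid analgesics are not recorded for randomised patients, so drift in their use between the sequential 0.4 and 0.3 mg/kg cohorts could not be separated from dose

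*Combined protocol and SAP*

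**What the plan says.** **Why 0.3 mg/kg is being tested.** The Amendment 3 rationale recalls that in the previous study "0.3mg/kg methadone was not effective in reducing postoperative opioid consumption". It then says "Currently, patients are prescribed additional drugs such as gabapentin and methocarbamol, with potential for interaction with all opioids", and concludes that "routine postoperative use of gabapentin and methocarbamol require re-evaluation of intraoperative methadone dosing" at 0.3 mg/kg. It also appeals to observations made so far under the current protocol.

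**What is recorded for randomised patients.**
- Section 7.2: "The inpatient medical record will be used to calculate the amount of morphine or morphine equivalents administered for each 24-hour period", plus oral opioids through discharge.
- Section 7.3: vital signs, weight, height and oxygen saturation at baseline.
- Section 7.5: "outpatient medications used, and chronic medical conditions will be obtained from the medical record at the time of enrollment".
- Sections 6.3.1 and 7.1: pain, sedation, itching and nausea scores.

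No section lists an inpatient non-opioid analgesic as a data item for these patients. Section 6.1 does mention pain treatment, but for those who decline randomisation: "If only participating in the questionnaire information regarding demographic data, pain scores and pain treatment will be collected".

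**Design and analysis.** The synopsis and section 6.1 randomise the first cohort 1:2 to control or 0.4 mg/kg, and the second 1:2 to control or 0.3 mg/kg. Section 6.4 leaves postoperative care to the treating team. Section 6.3.1 describes the research assessor as blinded; nothing is said about the treating team. Section 2 makes comparison of two doses an aim. Section 9.3.2 compares two or three groups and provides for adjustment for confounders without naming any.

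**The concern.** Opioid consumption is a primary outcome (section 9.1.1). A non-opioid drug that reduces opioid need lowers that outcome without appearing in it. The sponsor names two such candidates and uses them to justify a dose level, yet the plan gives no means of checking whether their use was the same in the groups being compared.

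The dose question is the one exposed. Patients on 0.4 and 0.3 mg/kg are treated in different periods, and randomisation does not balance what changes between periods. If adjunct use rose from the first cohort to the second, 0.3 mg/kg would look better relative to 0.4 mg/kg than it is; if use fell, the reverse. The adjustment allowed in section 9.3.2 cannot help with a variable that was never abstracted.

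**Working it through.** **1. The plan's own figure.** Section 9.3.1 gives a mean of 274 mg over 72 hours, SD 82 mg, a 30% reduction, two-sided alpha 0.05, and about 60 patients at 1:2 (20 control, 40 methadone).
- Target difference: 0.30 × 274 = 82.2 mg.
- Standard error: 82 × √(1/20 + 1/40) = 22.5 mg.
- Power: 94.9% by the noncentral t distribution (95.5% by the normal approximation).

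The stated power of at least 80% is met. The point here concerns data collection, not power.

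**2. Where drift enters.** Let a change in adjunct use lower opioid consumption by b mg in every second-cohort patient relative to the first cohort. Assume equal cohorts (10 control and 20 methadone each; the documents do not fix cohort sizes) and no true difference between doses.

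| Comparison | Shift in first group | Shift in second group | Bias |
|---|---|---|---|
| 0.3 v 0.4 mg/kg, direct | −b | 0 | −b |
| 0.3 mg/kg v pooled controls | −b | −b/2 | −b/2 |
| 0.4 mg/kg v pooled controls | 0 | −b/2 | +b/2 |
| Combined methadone v all controls | −b/2 | −b/2 | 0 |
| Either dose v its own cohort's controls | same as controls | same as methadone | 0 |

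The fourth row cancels because the allocation ratio is the same in both cohorts, so each cohort has the same weight in both arms. In practice it cancels only approximately, since achieved allocation may depart from 1:2 and the adjunct effect need not be the same in both arms.

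**3. Illustrative size.** The documents give neither an adjunct effect nor a usage rate, so both are assumed. Spurious difference = 274 × proportional opioid reduction × difference in adjunct use.
- Low: 274 × 0.20 × 0.10 = 5.5 mg; 5.5 / 82.2 = 7%.
- High: 274 × 0.30 × 0.30 = 24.7 mg; 24.7 / 82.2 = 30%.

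The table gives the chance of p < 0.05 when there is no true effect, with SD 82 mg and a two-sided t-test:

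| Spurious difference | 20 v 20 (direct dose comparison) | 20 v 40 (combined, if prescribing differs by arm) |
|---|---|---|
| 5.5 mg | 5.5% | 5.7% |
| 24.7 mg | 15% | 19% |

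Wider assumptions (10-30% reduction, 25-50 point difference) give 274 × 0.10 × 0.25 = 6.9 mg to 274 × 0.30 × 0.50 = 41.1 mg, with false-positive rates of 6-34% for 20 v 20 and 6-44% for 20 v 40.

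**4. Price of comparing doses through concurrent controls.** The contrast is (0.4 mg/kg − its controls) − (0.3 mg/kg − its controls).
- Standard error: 82 × √(1/20 + 1/10 + 1/20 + 1/10) = 44.9 mg, against 82 × √(1/20 + 1/20) = 25.9 mg for the direct comparison.
- Difference detectable with 80% power (2.80 × SE, normal approximation): about 126 mg against 73 mg.

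The protected comparison is √3 = 1.73 times less precise.

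**The case against.** The strongest objection is that Amendment 3 calls adjunct use routine. If nearly every patient receives these drugs, exposure is similar across arms, and across cohorts too if the practice was settled before the first one. The amendment places the change after the previous study ended; it does not say that practice changed between the present cohorts. This stands: drift is possible, not shown, and a large imbalance between arms is not the natural expectation.

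Several stronger readings are tempting but unsupported.
- **That an adjunct imbalance would be mistaken for a methadone effect in the main comparison.** The powered comparison combines the two methadone groups against control, and drift between cohorts largely cancels there. Chance imbalance within a cohort is already covered, on average, by alpha. Different prescribing after randomisation remains possible, but its direction is unknown: if control patients had more pain and received more adjuncts, the opioid difference would shrink. Prescribing that responds to pain control is also partly a consequence of assignment and not simple bias.
- **That postoperative care is given unmasked.** The documents state blinding for the research assessor and are silent on the treating team.
- **That adjuncts are shown to have changed opioid need.** The amendment speaks of a potential interaction; reduced need is a fair inference from it.
- **That more is collected from survey-only participants than from randomised patients.** Section 6.1 describes a reduced dataset for people who decline randomisation and does not define the full one.
- **That the information is lost.** The inpatient record already used in section 7.2 should hold it. What is missing is a plan to abstract it.

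**Conclusion.** The gap is real and specific. A factor the sponsor cites as a main reason for re-testing 0.3 mg/kg is not a data item for randomised patients. The 0.4 v 0.3 mg/kg comparison has no randomised protection against drift in that factor, and pooling controls across cohorts would carry half of any drift into each dose-versus-control contrast when cohorts are equal in size. The combined methadone-versus-control result is largely protected, with a residual question about differential prescribing whose sign cannot be given.

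The 5-25 mg range (7-30% of 82 mg) illustrates assumed adjunct effects and imbalances and is not a figure from the documents. Its lower end is negligible; its upper end needs both assumptions at their extreme. This is a worthwhile low-cost improvement, not a flaw that undermines the main comparison.

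**What to change.** 1. Extend section 7.2 to abstract, for randomised patients in both arms, every inpatient non-opioid analgesic and intraoperative adjunct: drug, dose and day.
2. Tabulate use by arm and by cohort.
3. State in section 9.3.2 that doses are compared through each cohort's concurrent controls and that controls are not pooled for dose-specific contrasts. Any direct 0.4 v 0.3 mg/kg comparison should be labelled non-randomised and read beside the adjunct table.
4. Keep the primary analysis unadjusted for adjunct use, which follows randomisation and may be affected by it. Report any adjunct-adjusted result only as a sensitivity analysis of the opioid outcome, and say whether that outcome covers 72 hours (as in the sample size calculation, section 9.3.1) or the whole hospital stay (section 9.1.1).

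**Cost.** A few more fields in a chart abstraction already being made, recoverable from the same record for patients already enrolled. Care does not change. The concurrent-control comparison is less precise (standard error about 45 mg against 26 mg with equal cohorts), so the dose comparison should be presented as an estimate with its interval.

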Study Design	Randomized, controlled, modified, Dixon up and down dose-finding design (1). Patients receive standard monitoring for anesthesia and postoperative care. Surgical and anesthesia (except for opioid use) care are not altered for study purposes. All patients are induced by propofol and muscle relaxants. In the first cohort, subjects are randomized 1:2 to either control (standard intraop opioid at anesthesiologists' discretion) or methadone HCl (0.4 mg/kg ideal body weight, IBW). Based on an interim analysis for the initial treatment dose (0.4mg/kg), the second cohort will be randomized 1:2 to either control (standard intraop opioid) or methadone HCl (0.3 mg/kg ideal body weight, IBW). Subjects in the study groups will receive methadone (IV bolus, after induction of anesthesia) as their primary intraoperative opioid, rather than leaving the choice of intraoperative opioid to the anesthesiologist. Intraoperative breakthrough pain will be treated at the discretion of the anesthesiologist with fentanyl. In the control groups, intraoperative opioid administration will be left at the discretion of the anesthesia providers. Patient controlled analgesia as prescribed by the clinical team, using hydromorphone or morphine, will be used to treat postoperative pain relief.
Inclusion and Exclusion Criteria	Inclusion Criteria 1. Age 11-18 years 2. Undergoing general anesthesia and idiopathic posterior spinal fusion surgery with anticipated postop inpatient stay of > 3 days 3. Signed, written, informed consent from legal guardians and assent from patient Exclusion Criteria 1. History of liver or kidney disease. 2. Females who are pregnant or nursing. 3. Developmental delay and/or neuromuscular scoliosis
Measurements	Total intraoperative and postoperative care unit (PACU) opioid administration will be recorded from the patient's medical record. Daily opioid consumption will be calculated from the PCA utilization and electronic medical records (EMRs) for up to 6 postoperative days. Pain intensity will be assessed using the Wong-Baker FACES scale. Pain relief is also assessed using a Colored-Visual Analog Scale. Blood and urine samples will be collected for 96 hrs after methadone dosing for determination of methadone and metabolite concentrations by HPLC-mass spectrometry. Subjects will be genotyped for major polymorphisms of the methadone metabolizing enzyme CYP2B6.

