9.2.4. Maximum plasma EDDP concentration

9.2.5. AUC (plasma EDDP)/AUC (plasma methadone)

9.2.6. Cmax (plasma EDDP)/Cmax (plasma methadone)

9.2.7. Urine concentration of methadone and EDDP

9.2.8. Side effects of opioids

9.3. Analysis.

9.3.1. Sample Size- we decided to use our pilot study data which looked into the pharmacokinetics of methadone in pediatric surgical patients attending St. Louis Children Hospital. This is actually the pooling place for the present study and therefore the information provided is a "true" sample of the data to be collected. The pilot study revealed that patients undergoing spinal fusion surgery used an average of 274 mg of morphine equivalents within 72 hours post-surgery with a standard deviation of 82 mg. Based on this information and assuming a 2-sided test of two independent sample means with α 0.05, we were able to estimate that the proposed study will have at least 80% power to detect 30% decrease in the total postoperative consumption of morphine or morphine equivalents among the patients assigned to the two treatment groups combined when compared to the control group

patients. Specifically, with a total sample of approx. 60 patients assigned equally across study groups (1:2 randomization), we will have adequate statistical power to detect a clinically meaningful reduction of opioid use in patients receiving a single dose of methadone before incision.

To study the effect size between two groups, power calculations were made with alternative mean differences in morphine consumption over 72 hours post-surgery with assumed variation range and a 2-sided test with $\alpha = 0.05$. Based on our conservative assumptions, we found that, with a sample as small as 20 in each group, we will have 80% power to detect a minimum difference between 10 and 20 mg of morphine use, depending on the observed variability between the two groups.

9.3.2. Statistical Analysis- Baseline characteristics of the cohort will be described. Demographics data including race, sex, and age at study entry will be analyzed using chi-square and t- test appropriate. Total daily opioid consumption and pain scores using both Wong-Baker FACES and colored visual analogue scale, will be compared between the groups. Outcome measures will be expressed by the mean and standard deviation. Group outcomes will be compared across the two or three groups, using t-test and/or analysis of variance, ANOVA and MANCOVA to account for potential cofounders.

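### No preoperative pain rating is named and rating of the day of surgery is left unstated, which costs the primary pain comparison some precision and leaves surgery-day opioid use without a matching pain score

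*Combined protocol and SAP*

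**What the plan says.** Section 9.1 lists two primary assessments: morphine-equivalent consumption during hospitalisation (9.1.1), and absolute pain and pain relief scores (9.1.2).

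- **Baseline.** Section 7.3: "Required baseline measurements that will be obtained from the EMR are vital signs, weight, height, and peripheral oxygen saturation by pulse oximetry". Pain is not in the list.
- **Preoperative contact.** Section 6.1: "Parents and patients will be asked to complete a questionnaire prior to" the operation. That questionnaire is described as covering anxiety and socioeconomic factors. Amendment 1 describes the tablet PROMIS questionnaire as covering expectations and functional status. Neither description names a pain score.
- **Postoperative ratings.** Section 6.3.1, on ratings by a blinded member of the research team: "These will be conducted on each post-operative day until discharge or post op day 6". Section 7.1 has pain intensity assessed each postoperative hospital day for at most six days.
- **Early opioid use.** Synopsis, Measurements: "Total intraoperative and postoperative care unit (PACU) opioid administration will be recorded" from the medical record. Section 7.2 totals opioid for each 24-hour period.
- **Record pain scores.** Section 6.1 collects these for questionnaire-only participants. Section 7.1 says nurses already score pain on the inpatient units. No text commits to using nursing scores for randomised patients.
- **Analysis.** Section 9.3.2 plans t-tests, ANOVA and MANCOVA, and names no covariates.

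**The concern.** Two things the pain analysis would benefit from are not secured.

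The first is a preoperative pain value. The plan intends covariate adjustment, yet the most obvious covariate for a pain score is not among the data it names, although patients are already seen before surgery. In a trial of about 60 patients, a useful covariate is worth having.

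The second is a pain score for the hours just after surgery. Postoperative analgesia is patient-controlled, so patients can trade pain against opioid, and the two primary assessments need to be read together over the same period. If the first pain rating is on day 1, lower opioid use in the recovery unit or on the first night could not be shown to have come without worse pain.

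**Working it through.** **The plan's own figure.** Section 9.3.1 gives power for the opioid outcome only. The inputs are:

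- pilot patients "used an average of 274 mg of morphine equivalents within 72 hours post-surgery with a standard deviation of 82 mg"
- "assuming a 2-sided test of two independent sample means with α 0.05"
- "with a total sample of approx. 60 patients assigned equally across study groups (1:2 randomization", read here as 20 control and 40 methadone

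The difference is 0.30 × 274 = 82.2 mg, or 82.2/82 = 1.00 SD. The standard error in SD units is √(1/20 + 1/40) = √0.075 = 0.274. Power is Φ(1.002/0.274 − 1.960) = Φ(1.70) = 95.5%, or 94.9% by the noncentral t. The claim that "the proposed study will have at least 80% power to detect 30% decrease in the total postoperative consumption of morphine or morphine equivalents" is therefore met as a lower bound. No effect size, SD or power is given for pain, so this point changes no stated sample size.

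**Precision for pain.** In SD units of the pain score, at 80% power and two-sided 0.05:

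- unadjusted detectable difference = (1.960 + 0.842) × 0.274 = 0.77 SD
- with a baseline covariate of correlation ρ, multiply by √(1 − ρ²)
- equivalent unadjusted sample = 60/(1 − ρ²)

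The documents give no ρ, so it is an assumption, shown as a range.

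| Assumed ρ | Residual variance | Detectable difference | Power at 0.77 SD | Equivalent N |
|---|---|---|---|---|
| 0 | 1.00 | 0.77 SD | 80% | 60 |
| 0.2 | 0.96 | 0.75 SD | 82% | 62.5 |
| 0.3 | 0.91 | 0.73 SD | 84% | 66 |
| 0.5 | 0.75 | 0.66 SD | 90% | 80 |

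**What is still attainable.** Amendment 3 refers to observations under this protocol to date, so some patients are already enrolled without a rating. If a fraction f of patients has a baseline and the rest carry a missing indicator, the average residual variance is about 1 − fρ². With f = 0.5, again an assumption:

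- ρ = 0.2: variance 0.98, detectable difference 0.767 × √0.98 = 0.76 SD
- ρ = 0.5: variance 0.875, detectable difference 0.767 × √0.875 = 0.72 SD

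**Which days are rated.** Section 6.3.1 ends at day 6 and section 7.1 allows at most six days. Days 1 to 6 are six days and fit both. Days 0 to 6 would be seven, against 7.1. Days 0 to 5 would stop short of the last day in 6.3.1. Days 1 to 6 is thus the natural reading, but neither section states a first day or a clock time, or expressly excludes the evening of surgery.

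**The case against.** The strongest reply is that nothing here threatens validity. The outcome is the absolute score, and randomisation makes that comparison fair without a baseline. This stands. A reader might infer that the primary pain comparison is compromised or cannot be adjusted at all. The documents do not support that: MANCOVA is planned, and other covariates can enter it. Nor do they show that no preoperative pain value exists, because the PROMIS items are not listed.

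A second reply is that the surgery-day gap is an ambiguity. This also stands. Both sections speak of the postoperative period or postoperative hospital days, which could include the hours after surgery. A flat statement that ratings start the next day goes too far, but a primary assessment should not leave its first time point open.

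Third, the correlation is assumed. At 0.2 the gain is about 4%, and early enrolment reduces it further. This stands, and it limits the size of the point.

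A reader might also take the half-life of 24 to 36 hours and the rapid redistribution described in the Background, and treat the fall in drug level before a day-1 rating as lost pain effect. The documents do not allow this. They give no rating time and no time course of analgesia, and the highest levels occur under anaesthesia, when pain cannot be self-reported. The stated rationale is long-lasting relief, which multi-day ratings suit.

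Finally, nothing shows that nurses record sedation or nausea scores, or that the recovery unit uses these pain scales. The remedy has to allow for that.

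**Conclusion.** The point holds as a modest, inexpensive improvement. No preoperative pain rating is named, and no surgery-day pain score is secured for randomised patients. The comparison of absolute scores remains valid.

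The precision at stake is a 4 to 25% reduction in residual variance, with the detectable difference moving from 0.77 SD to between 0.75 and 0.66 SD. This rests on an assumed correlation of 0.2 to 0.5, a 20 against 40 comparison, and baselines for everyone. With baselines for only half the patients, the range is about 0.76 to 0.72 SD.

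The second loss cannot be put as a number from these documents, but it bears more on interpretation: surgery-day opioid use could not be set against pain over the same hours. It should not be expressed through drug levels, and the surgery day should be called unstated, not excluded.

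**What to change.** 1. **Preoperative rating, for remaining patients.** Add one FACES pain-intensity rating at the existing questionnaire contact. Name it as a covariate in the pain-intensity model, with cohort also in the model and a missing-baseline indicator for earlier patients. Missingness then follows enrolment date, not arm; if it coincides with the first cohort, the indicator and the cohort term are the same and one is dropped. Add a coloured-scale rating only if that scale measures pain intensity. The synopsis and 6.3.1 call it a relief scale, while 7.1 and 9.3.2 treat it as a pain scale. The plan should settle which, since relief of postoperative pain has no preoperative value.
2. **Day of surgery.** State in 6.3.1 and 7.1 whether day 0 is rated. For all randomised patients in both arms, extract nursing pain scores for the recovery unit (where recorded) and the first night from the medical record, as section 6.1 already plans for questionnaire-only participants. Include sedation and nausea only where the record contains them. Report day 0 separately from the research ratings.

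The cost is about a minute per patient before surgery, plus chart abstraction. The day-0 scores would not be assessor-blinded, because the blinding in 6.3.1 covers only the research team's ratings. For patients already enrolled, only the chart part can be recovered. No care is altered.
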